---

# Modification

Basic Info	
Confirmation Number:	chigbiga
Protocol Number:	829476
Created By:	[name]
Principal Investigator:	[name]
Protocol Title:	Validation of Point of Care of Liver Function Testing
Short Title:	Validation POC-LFT
Protocol Description:	This study is to test the accuracy of a point of care device that tests liver function. The target population is adults who have an indication to collect a liver function panel that will be drawn on the same day as their clinic visit or during their inpatient hospital admission. Participants will receive a finger prick and blood will be place on point of care device. Results will be compared to results from traditional blood draw.
Submission Type:	Biomedical Research
Application Type:	FULL

## PennERA Protocol Status

Approved

Resubmission\*

No

Are you submitting a Modification to this protocol?\*

Yes

## Current Status of Study

Study Status

Currently in Progress

*If study is currently in progress, please enter the following*

Number of subjects enrolled at Penn since the study was initiated

0

Actual enrollment at participating centers

0

*If study is closed to further enrollment, please enter the following*

Number of subjects in therapy or intervention

0

**Number of subjects in long-term follow-up only**

0

**IRB Determination**

If the change represents more than minimal risk to subjects, it must be reviewed and approved by the IRB at a convened meeting. For a modification to be considered more than minimal risk, the proposed change would increase the risk of discomfort or decrease benefit. The IRB must review and approve the proposed change at a convened meeting before the change can be implemented unless the change is necessary to eliminate an immediate hazard to the research participants. In the case of a change implemented to eliminate an immediate hazard to participants, the IRB will review the change to determine that it is consistent with ensuring the participant's continued welfare. Examples: Convened Board Increase in target enrollment for investigator initiated research or potential Phase I research Expanding inclusion or removing exclusion criteria where the new population may be at increased risk Revised risk information with active participants Minor risk revisions that may affect a subject's willingness to continue to participate Expedited Review Increase in target enrollment at Penn where overall enrollment target is not exceeded or potentially sponsored research Expanding inclusion or removing exclusion where the new population has the same expected risk as the previous, based on similarities of condition Revised risk information with subjects in long-term follow-up Minor risk revisions with no subjects enrolled to date Expedited Review

**Modification Summary**

Please describe any required modification to the protocol. If you are using this form to submit an exception or report a deviation, enter 'N/A' in the box below.

This modification is to expand recruitment to include patients admitted to inpatient services at The Hospital of the University of Pennsylvania.

**Risk / Benefit**

Does this amendment alter the Risk/Benefit profile of the study?

No

**Change in Consent**

Has there been a change in the consent documents?

No

**If YES, please choose from the options below regarding re-consenting**

**Deviations**

**Are you reporting a deviation to this protocol?\***

No

**Exceptions**

**Are you reporting an exception to this protocol?\***

No

# Protocol Details

Resubmission\*  
Yes

### Responsible Org (Department/School/Division):

4237 - DM-Gastroenterology

### Key Study Personnel

None

### Disclosure of Significant Financial Interests\*

Does any person who is responsible for the design, conduct, or reporting of this research protocol have a **FINANCIAL INTEREST**?

No

### Penn Intellectual Property\*

To the best of the Principal Investigator's knowledge, does this protocol involve the testing, development or evaluation of a drug, device, product, or other type of intellectual property (IP) that is owned by or assigned to the University of Pennsylvania?

No

### Certification

I have reviewed the *Financial Disclosure and Presumptively Prohibited Conflicts for Faculty Participating in Clinical Trials* and the *Financial Disclosure Policy for Research and Sponsored Projects* with all persons who are responsible for the design, conduct, or reporting of this research; and all required Disclosures have been attached to this application.

Yes

## Biomedical Research

### Clinical Trial\*

Is this a clinical trial?

Yes

If Yes, please be aware that for each clinical trial conducted or supported by a Federal department or agency, one IRB-approved informed consent form used to enroll subjects must be posted by the awardee or the Federal department or agency component conducting the trial on a publicly available

Federal Web site that will be established as a repository for such informed consent forms.

**Investigator Initiated Trial\***

Is this an investigator initiated trial?

Yes

If Yes, please be aware that the investigator may be required to create and manage a record of this trial in <https://clinicaltrials.gov>.

**Drugs or Devices\***

Does this research study involve Drugs or Devices?

Yes: Investigational devices that may qualify as Non-Significant Risk.

**IND Exemption**

**For studies that fall under an IND exemption, please provide the number below**

**For studies including IND or IDE's, please provide the number(s) below**

**IDE Review\***

NOTE: For research involving investigational devices, you are required to review the guidance on Managing Research Device Inventory. Consult the Penn Manual for Clinical Research: <https://somapps.med.upenn.edu/pennmanual/secure/pm/investigational-product-management> Please check the box Yes if you have reviewed the guidance.

Yes

**Research Device Management\***

Please indicate how research device(s) will be managed.

The device receipt, storage and dispensing is being conducted by the research team (please provide information in the protocol summary as to how this will be conducted)

**Drug, Herbal Product or Other Chemical Element Management \***

Please indicate how drugs, herbal products or other chemical entities will be managed.

Not Applicable (no drugs, herbal products or other chemical entities)

**Radiation Exposure\***

Are research subjects receiving any radiation exposure (e.g. X-rays, CT, Fluoroscopy, DEXA, pQCT, FDG, Tc-99m, etc.) that they would not receive if they were not enrolled in this protocol?

No

**Gene Transfer\***

Does this research involve gene transfer (including all vectors) to human subjects?

No

**Human Source Material\***

Does this research include collection or use of human source material (i.e., human blood, blood products, tissues or body fluids)?

Yes

**CACTIS and CT Studies\***

Does the research involve Center for Advanced Computed Tomography Imaging Services (CACTIS) and CT studies that research subjects would not receive if they were not part of this protocol?

No

**CAMRIS and MRI Studies\***

Does the research involve Center for Advanced Magnetic Resonance Imaging and Spectroscopy (CAMRIS) and MRI studies that research subjects would not receive if they were not part of this protocol?

No

**Investigational Agent or Device within the Operating Room\***

Does the research project involve the use of an investigational agent or device within the Operating Room?

No

**Cancer Related research not being conducted by an NCI cooperative group\***

Does this protocol involve cancer-related studies in any of the following categories?

No

**Processing of Materials\***

Will the research involve processing (such as over encapsulating, or compounding)?

No

**In-House Manufacturing of Materials\***

Will the research involve processing (such as over encapsulating, or compounding)?

No

**Medical Information Disclosure\***

Does the research proposal involve the use and disclosure of research subject's medical information for research purposes?

Yes

If the answer is YES, indicate which items is is provided with this submission:

Modified research informed consent document that incorporates HIPAA requirements

**CTRC Resources\***

Does the research involve CTRC resources?

No

**Pathology and Laboratory Medicine Resources\***

Will samples be collected by hospital phlebotomy and/or processed or analyzed by any of the clinical laboratories of the University of Pennsylvania Health System?

No

**Research Involves Apheresis, Cell Collection, and/or Blood Product Collection\***

Does this research involve collection of blood products in the Penn Donor Center and/or the use of apheresis for treatment or collection of cells or other blood components?

No

**Research involving blood transfusion or drug infusions\***

Will your research involve blood transfusion or infusion of study drug in 3 Ravdin Apheresis Unit for research purposes?

No

**Trial in Radiation Oncology**

Is this research a prospective trial being done in Radiation Oncology, and if so, has this protocol been approved by the Radiation Oncology Protocol committee?

N/A

**Study in Radiation Oncology**

Is this research a retrospective study being done in Radiation Oncology, and if so, has this project been reviewed by the Radiation Oncology Clinical Research Group?

N/A

**Use of UPHS services\***

Does your study require the use of University of Pennsylvania Health System (UPHS) services, tests or procedures\*, whether considered routine care or strictly for research purposes?

No

**Primary Focus\***

Tissue/biospecimen

**Protocol Interventions**

 Sociobehavioral (i.e. cognitive or behavioral therapy)
 Drug
 Device - therapeutic
 Device - diagnostic (assessing a device for sensitivity or specificity in disease diagnosis)
 Surgical
 Diagnostic test/procedure (research-related diagnostic test or procedure)
 Obtaining human tissue for basic research or biospecimen bank
 Survey instrument
 None of the above

The following documents are currently attached to this item:

*There are no documents attached for this item.*

**Department budget code**

000 - 000 - 0 - 000000 - 0000 - 0000 - 0000

**Funding Sponsors**

**Funding sponsors billing address**

If you have selected a commercial or industry sponsor, please provide the appropriate address and contact information for the Sponsor for the purposes of billing for IRB review fees (initial review, continuing review and convened modification fees apply here). If the Sponsor is not industry/commercial, this information is not necessary to provide with your application.

**Funding sponsors gift**

Is this research being funded by a philanthropic gift?

**Regulatory Sponsor**

**IND Sponsor**

none

000 - 000 - 0 - 000000 - 0000 - 0000 - 0000

**Industry Sponsor**

None

**Project Funding\***

Is this project funded by or associated with a grant or contract?

Pending

**Sponsor Funding**

Is this study funded by an industry sponsor?

No

**Status of contract**

---

**The following documents are currently attached to this item:**

*There are no documents attached for this item.*

## Multi-Site Research

**Other Sites**

No other sites

**Management of Information for Multi-Center Research**

**The following documents are currently attached to this item:**

*There are no documents attached for this item.*

## Protocol

**Abstract**

We are testing the accuracy of a point of care device that tests liver function within 20 minutes at a doctors office for FDA approval documentation. The target population is any patient who have an indication to perform liver function tests. Any adult patient who has been seen by a liver specialist and/ or been prescribed liver function testing to be drawn on the same day of their clinic visit or inpatient admission is eligible to participate in the trial. Their finger will be pricked and blood placed on the device. Results will be compared to results from traditional blood draw.

**Objectives****Overall objectives**

1. To obtain regression curves and a correlation coefficient to compare standard blood draws to the investigational diagnostic device.

**Primary outcome variable(s)**

Regression curve and correlation coefficient

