coverage, and provider. Given that over two-thirds of all clinical decisions are based on laboratory testing (COLA, 2015) and in a 2002 survey of the US, 77% of providers were unable to contact their patients with abnormal diagnostic results (White, 2002), diagnostics are not working efficiently for outpatient providers. These studies show that lack of access to fast point of care results leads to significant problems in continuum of care and effective care. Very few point of care (POC) diagnostics are used by doctors, as modular machines are often cost or workflow prohibitive. Many POC diagnostics require a trained technician and have high cost hardware and certifications. The POC diagnostics that are often used are tests such as pregnancy tests or rapid strep tests that are multiple different platforms and are rate-limited in how many tests a practice can adopt. Group K is revolutionizing healthcare through innovative POC diagnostics. We solve the inefficiencies of current lab solutions by bringing the "lab" to the provider and allowing practitioners to run diagnostic tests onsite in doctors offices and clinics. With a low cost, reliable system providers have actionable information before the patient leaves the office. Doctor offices will be able to pay a low cost for the product and bill insurers for running diagnostics. Group Ks quick, inexpensive, and accurate diagnostic platform will be able to improve care for patients all around the world. Group K is developing a paper microfluidic platform with an accompanying mobile application(app). The paper microfluidic device is a simple, inexpensive wax backed device with three testing areas. These areas have a mix of dried proprietary reagents that when combined with a patients drop of blood, or in the future, saliva or urine, will produce results in a color change. An app is then used to interpret the color change and output results to a doctor.

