#### **Design**

The design of the study is to investigate 200-400 patient finger prick samples to prove the ability of Group Ks Diagnostic app to identify liver function values on the multidiagnostic. The values will be stored on a Penn Server correlating the patient data obtained from the multidiagnostic with a random code, and then the random code correlated to the patient identifier (name and date of birth) and then the patients record of the results of their standard liver function test.

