## **Characteristics of the Study Population**

#### **Target population**

The target population is adults (18 years and old) with varying liver health who have had a hepatic function panel or equivalent tests completed at the same day as their finger prick sample obtained; ALT, AST, ALP, albumin, bilirubin and total protein.

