### **Analysis Plan**

Lowest level frequency of detection must be detected 90% of the time. This will become the functional lower limit. The same with the highest level of frequency. We will exclude any data from tests that did not follow standard operating procedures or were not performed in a controlled, laboratory setting as well as any blood that has expired before liver function tests were completed. Each data point will represent one observation or one test run. We will use regression methods to determine the linear relationship between standard lab results and Group K diagnostic's device. We will also determine the correlation coefficient and measure of scatter around the regression line. This will be shown in equation form and in the form of graphs. The dependent variable will be our test results, the independent variable the standard of care.

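### The aim is accuracy against the laboratory, but one of the two primary outcomes is a correlation coefficient, which does not measure accuracy

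*Protocol*

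**What the plan says.** The protocol gives its purpose twice as accuracy. The Protocol Description says "This study is to test the accuracy of a point of care device that tests liver function", and the Abstract says "We are testing the accuracy of a point of care device". In both places the comparator is the conventional blood draw.

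The single listed objective is "To obtain regression curves and a correlation coefficient to compare standard blood draws to the investigational diagnostic device". The primary outcome is "Regression curve and correlation coefficient", two items with no weighting between them. The secondary outcome mentions consistent accuracy but gives no metric for it.

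The Analysis Plan states: "We will use regression methods to determine the linear relationship between standard lab results" and the device. The device result is the dependent variable and the laboratory result the independent one. It adds the correlation coefficient and a measure of scatter about the regression line, reported as an equation and in graphs. It mentions no device-minus-laboratory difference, no limits of agreement, no scatter about the line of identity, and no comparison of slope and intercept with 1 and 0.

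The target population is adults "with varying liver health who have had a hepatic function panel or equivalent tests completed", with no distribution of values specified. The planned size is 200-400 finger-prick samples (Design).

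**The concern.** The Background says the device is to be used so that "providers have actionable information before the patient leaves the office". For that use, what matters is how far a reading lies from the laboratory value. The correlation coefficient does not say. It is unaffected by constant or proportional bias, and for a fixed device error it depends on how widely the patients' values are spread. Scatter about the fitted line is unaffected by constant bias, so on its own it does not measure accuracy either.

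At stake is how the headline result is read. A biased and an unbiased device can share the same r, and one device can show quite different r in two patient groups. The current modification adds inpatients to the clinic population, so the spread of values, and r with it, could change with no change in the device. A reader who takes r as primary evidence could credit the device with accuracy that r does not show.

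**Working it through.** The protocol gives no target correlation, SD, device error, power or acceptance limit, so there is no stated figure to reproduce. Every patient mean, spread, device error and bias below is an assumption. The algebra does not depend on them. All examples are on the raw scale, because the Analysis Plan describes a linear relationship and no transformation. Only the 200-400 samples come from the protocol.

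**General fact.** For any constant a and any b > 0, the correlation of x with a + b·y equals the correlation of x with y. Adding a to the device reading also leaves the residual SD about the fitted line unchanged. Multiplying the reading by b multiplies that SD by b.

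**(a) Constant bias.** Assume albumin with patient SD 0.6 g/dL and error SD 0.15 g/dL.
- r = 0.6 / √(0.6² + 0.15²) = 0.970 for any constant bias.
- Scatter about the line = 0.15 g/dL for any constant bias.
- Root-mean-square difference = √(bias² + 0.15²), which is 0.15 g/dL with no bias and √(1.0² + 0.15²) = 1.01 g/dL with a bias of +1.0.
- The intercept, 0 or 1.0, would show the bias.

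**(b) Proportional bias.** Assume laboratory values are lognormal with median 50 U/L, and device = k × laboratory × (1 + error), with error SD 10% and k = 1 or 2.
- r = 1 / √(1 + 0.01 × e^(s²) / (e^(s²) − 1)), where s is the log SD. The factor k cancels.
- s = 0.5: r = 1 / √1.0452 = 0.978. s = 1.0: r = 1 / √1.0158 = 0.992.
- In 2000 simulated studies of 400 pairs, mean r was 0.978 and 0.992 for both values of k. Mean slopes were 1.00 and 2.00, so the slope would show the bias.

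**(c) Patient spread.** Assume one unbiased device with error SD 0.3 g/dL. r = s / √(s² + 0.3²), where s is now the patient SD, and the limits of agreement are ±1.96 × 0.3.

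| Patient SD (g/dL) | r | 95% limits of agreement (g/dL) |
|---|---|---|
| 0.3 | 0.71 | ±0.59 |
| 0.6 | 0.89 | ±0.59 |
| 0.9 | 0.95 | ±0.59 |

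**(d) Independent check with other inputs.** Lognormal laboratory values, median 40, log SD 0.6; device = a + b × (laboratory + error), error SD 8; 200,000 simulated pairs.

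| Device | r | Scatter about line | Mean difference | 95% limits of agreement |
|---|---|---|---|---|
| Unbiased | 0.969 | 8.0 | 0 | −15.7 to 15.7 |
| Reads 20 high | 0.969 | 8.0 | 20 | 4.3 to 35.7 |
| Reads 1.5 × | 0.969 | 12.0 | 24 | −14.9 to 62.8 |
| Reads 0.5 × | 0.969 | 4.0 | −24 | −55.9 to 8.0 |

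r does not separate the four devices. Scatter about the line is smallest for the device that halves every value.

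**(e) Is the planned sample enough for an agreement analysis?** Assume one pair per patient and express results in units of the SD of the differences.
- Mean difference: 95% CI half-width = 1.96 / √n, which is 0.14 SD at n = 200 and 0.10 SD at n = 400.
- Each limit of agreement: 1.96 × √(1/n + 1.96² / (2(n − 1))), which is 1.96 × 0.121 = 0.24 SD at n = 200 and 1.96 × 0.0855 = 0.17 SD at n = 400.

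**The case against.** The strongest reply is that the planned outputs already contain the information. Under the linear model with intercept a and slope b, the mean difference is a + (b − 1) × laboratory mean, and the variance of the differences is (b − 1)² × laboratory variance + residual variance. In example (a), intercept 1.0, slope 1 and scatter 0.15 give limits of 1.0 ± 1.96 × 0.15, or 0.71 to 1.29 g/dL. In none of the examples would the full set of outputs hide the bias. This stands, and it limits the point: the plan is not blind to bias, and scatter about the line is a fair measure of random error. It does not justify r as a primary outcome, and the Analysis Plan does not say that the equation will be judged against slope 1 and intercept 0.

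A second reply is that accuracy is the secondary outcome and that a statistical analysis plan, not shown here, may supply the metrics. Detail may well be left to that plan. But the protocol itself fixes r as primary and ranks accuracy, the study's stated purpose, below it.

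Third, no threshold or success claim is attached to r, so the harm depends on a reader giving r weight that the equation beside it would correct. That is fair, and it is why the point is not more serious. It is also fair that limits of agreement show how large the differences are, not whether they are small enough. That judgement needs an allowable error.

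**Conclusion.** The concern holds and should be fixed. The protocol names a correlation coefficient as one of two primary outcomes for a study of accuracy, and it states no analysis that directly reports how far the device lies from the laboratory. In the illustrations, r stays at 0.970 while the root-mean-square difference goes from 0.15 to 1.01 g/dL, and r moves from 0.71 to 0.95 while the limits of agreement stay at ±0.59 g/dL. Those sizes rest on assumed spreads, errors and biases. The insensitivity of r to shift and scale does not.

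The fault is in the choice of headline measure, not in the data to be collected. The regression equation would let a careful reader recover the bias.

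**What to change.** Revise Overall objectives, Primary outcome variable(s) and Analysis Plan as follows:
- **Primary, for each analyte:** the mean device-minus-laboratory difference and the 95% limits of agreement, each with confidence intervals, on a log or percent scale where scatter grows with concentration.
- **Regression:** keep it, reporting slope and intercept with confidence intervals read against 1 and 0.
- **Correlation coefficient:** keep it as descriptive only.

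The allowable error against which the limits are judged can be set in the statistical analysis plan.

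The change uses the same 200-400 pairs, with no extra patients or procedures and only slightly more analysis. It does alter the primary outcome of an approved protocol, so it needs a modification. Current Status of Study records no subjects enrolled, so at this submission it could be made before any data existed. The other cost is that the headline figure may look less favourable than r.
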